APPENDIX 3: SCHEDULE OF EVENTS

Mechanism to Execute	Epochs	Screening/Baseline** Day 1 must be completed on same day	Week 4 Day 28 ±3	Week 8 (EOT/ET) Day 56 ±3
Clinical Outcome Assessments			Intervention Period	
In-person by site staff	Randomization *After the following assessments are completed and patient meets all I/E Criteria	X		
In-person by blinded site staff via tablet or paper copy	Informed Consent	X		
In-person by blinded site staff for input in EDC	Inclusion/Exclusion Criteria	X		
In-person by blinded site staff for input in EDC	Demographics	X		
In-person by blinded site staff for input in EDC	Previous Medications	X		
In-person by blinded site staff for input in EDC	Psychiatric History	X		
In-person by blinded site staff/PI via tablet	SCID-5-CT^{a, e}	X		
Hybrid by blinded site staff/PI for input in EDC	Concomitant Medications and Therapy *Post randomization, will rely on self-report from participant on continued TAU	X	X	X
Hybrid by blinded site staff/PI for input in EDC	Pregnancy History and Status *Post randomization, will rely on self-report from participant on pregnancy status	X	X	X
Virtual by blinded CIR	HAM-D17^c *Primary endpoint is HAM-D 6 derived from HAM-D17	X	X	X

Sponsor Name: Woebot Health

Protocol Number: WB001-001

Hybrid by blinded site staff/PI	C-SSRS^a *Safety endpoint and will be administered virtually by PI if safety event is flagged and confirmed	X	X	X
Self-report via link	EPDS^b *If safety flag is raised due to score of >2 on item #10, EPDS, PI/site staff are notified immediately for review, and action, if needed	X	X	X
Self-report via link	PHQ-9^b *If safety flag is raised due to score of ≥ 2 on item #9, PHQ-9PI/site staff are notified immediately for review and action	X	X	X
Self-report via link	GAD-7^b	X	X	X
Hybrid by blinded site staff/PI into EDC	CGI-S^a	X	X	X
Virtual by blinded site staff/PI into EDC	CGI-I^a		X	X
Self-report via link	PGI- S^b	X	X	X
Self-report via link	PGI- C^b		X	X
Self-report via link	MIBS^b	X	X	X
Self-report via link	Healthcare Utilization	X	X	X
Self-report via link	Program Assignment Assessment (Blinding)			X
Hybrid by blinded site staff/PI into EDC	AEs/SAEs Assessment^a *Includes confirming no recent hospitalizations for mental health-related incidence	X	X	X
Self-report via link	CSQ-8^b			X
Virtual by blinded PI	Escalation Trigger Follow-Up		X ^d	

Sponsor Name: Woebot Health

Protocol Number: WB001-001

AE = adverse event; BL = baseline; CGI-I = Clinical Global Impression of Improvement; CGI-S = Clinical Global Impression of Severity; C-SSRS = Columbia-Suicide Severity Rating Scale; CSQ = Customer Satisfaction Questionnaire; EOT = end of treatment; EPDS = Edinburgh Postnatal Depression Scale; ET= Early Termination visit; GAD = Generalized Anxiety Disorder Questionnaire; HAM-D = Hamilton Depression rating scale; MIBS = Mother-to-Infant Bonding Scale; PHQ = Patient Health Questionnaire; PGI-C = Patient Global Impression of Improvement of Change; PGI-S = Patient Global Impression of Disease Severity; SCID-5-CT = Structured Clinical Interview for DSM-5 - Clinical Trials Version; Hybrid = indicates conducted in-person at BL and virtual by participant post-randomization through link; CIR = Central Independent Rater;

^a These assessments will be administered by blinded investigator or qualified designee (e.g., sub-investigator, or dually qualified site staff).

^b These assessments will be self-administered and completed independently by participant s as a link (± 3 days of visit date)

^c Will be administered by a CIR

^d Any confirmed Escalation trigger through the following three scenarios will result in PI-administered C-SSRS:

- [REDACTED]
- [REDACTED]
- [REDACTED]
- [REDACTED]
- [REDACTED]

^e Only includes modules for major depressive disorder (MDD), current and lifetime diagnosis of a psychotic disorder including postpartum psychosis and Schizophrenia, bipolar disorder, homicidal or infanticidal ideation, and history of drug and/or alcohol

AE/SAE collection will begin at the time ICF is signed. AEs/SAEs should be recorded until the EOT visit.

*Note: the HAM-D will be administered as the Structured Interview Guide for the Hamilton Depression Rating Scale – 17 item version (SIGH-D 17-item HAM-D) to derive the HAM-D6 as the primary endpoint

**Final Screening and Baseline visit assessments must be completed on the same day.

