- Change from baseline in Clinical Global Impression-Improvement (CGI-I) the CGI-Severity (CGI-S) at Week 4 and Week 8
- Change from baseline in Patient Global Impression-Change (PGI-C) and Patient Global Impression-Severity (PGI-S) at Week 4 and Week 8
- Client Satisfaction Questionnaire-8 at Week 8

Safety Endpoints: C-SSRS and Adverse Events (AEs), Serious Adverse Events (SAEs)

Safety Aim: To evaluate the safety of [WB001+TAU] versus [ED001+TAU] based on PI and Sponsor determined AE and SAEs. The study will use the Columbia-Suicide Severity Rating Scale (C-SSRS), the PHQ-9 item #9, and the EPDS item #10, and the HAM-D17 item #3 to facilitate identification of AEs and SAEs. It would be separately determined whether identified AEs or SAEs are related to the device.

Statistical Methods: The primary efficacy endpoint is the difference between treatment arms in the HAM-D6 score at Visit Week 8 after controlling for baseline and other covariates. For the ITT population, a restricted maximum likelihood (REML) based linear MMRM approach will be used to test for systematic differences in change between arms over time, after accounting for participant-specific heterogeneity in HAM-D6 scores residual error structure. The MMRM will be parameterized to include random effects for site and repeated measures for post-baseline visits using an unstructured residual covariance structure (3 parameters); in the unlikely event that the unstructured covariance matrix fails to converge, the model will be refit with a first order autoregressive covariance matrix (2 parameters).

Sponsor Name: Woebot Health

Protocol Number: WB001-001

This test will be performed using the final, MMRM model-based t-test with a two-sided significance level of 5%. Estimated least squares means for change from baseline and the observed absolute values (\pm SE) at each visit by treatment group will be plotted over time.

No explicit imputation will be performed; the MMRM model described above will be run on this population, which implicitly imputes missing data under a missing at random (MAR) assumption.

As a sensitivity analysis for the primary analysis using ITT population, MMRM model in the same manner as described above will be conducted in the PP population.

The treatment effectiveness on MIBS, EPDS, PHQ-9, and GAD-7 (difference between arms at Week 8, controlling for baseline) will be evaluated using the same analysis plan proposed for the analysis of the primary endpoint (HAM-D6).

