However, potential risks include the opportunity cost of seeking alternative treatment, device software failure, leading to delayed access, information security breaches, and potentially brief emotional stress that may result from attending key assessment visits, completing survey questions that cover sensitive topics, and discontinued access to the assigned study intervention at the end of study (Week 8).

Several aspects of the study design will mitigate these potential risks of participating in the study:

- [REDACTED]
- adjunct.
- The eligibility criteria will exclude patients with severe psychiatric diagnoses (e.g., psychosis, history of attempted suicide or current suicidal ideation, substance use disorder).
- Concomitant medications and psychotherapy are allowed during the study period per standard of care as prescribed and administered by trained professionals, as long as the medication doses and frequency of psychotherapy are stable for at least 4 weeks before the Baseline visit. The study will capture any changes (e.g., starting or stopping a medication or any change in medication dose or frequency, as well as changes in frequency of psychotherapy).
- [REDACTED]

Sponsor Name: Woebot Health

Protocol Number: WB001-001

- Survey Questionnaires have been thoughtfully selected to minimize the risk of emotional upset due to the topics covered.
- Woebot performing appropriate software verification and validation testing to demonstrate that the device's behavioral therapy has been correctly implemented so that the participant can access it when needed.
- All study data will be gathered on a secure Health Insurance Portability and Accountability Act (HIPAA)-compliant web platform and will be encrypted to minimize the risk of a data breach.
- Participants will be informed that they may leave the study at any time and can receive appropriate referrals for alternative treatment.
- Participants will have contact with the investigator and/or designated clinical rater at each study assessment time point, who will administer validated psychometric assessments to monitor for worsening symptoms and/or the development of suicidal ideation.
- Study withdrawal criteria are designed so that participants who experience worsening of symptoms can withdraw from the study to receive additional treatment, per PI recommendation.

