Participants will attend a mid-study and EOT (at Week 4 and Week 8) telehealth visit with a CIR, to be assessed based on the HAM-D, a validated standard clinician-rated and participant-rated outcome scales for PPD. Any AE/SAE raised during CIR-administration of HAM-D, will be raised to the PI or qualified designee for final determination on appropriate course of action. At Week 4 and Week 8 the PI or qualified site staff will

Sponsor Name: Woebot Health

[figure not shown]
Protocol Number: WB001-001

administer the C-SSRS, evaluate for concomitant medications/therapy, pregnancy status, and safety throughout the duration of the trial.

At Week 4 and 8, participants will be prompted to complete several online self-report assessments (e.g., EPDS, PHQ-9, MIBS, GAD-7 and PGI) within 3-days prior to or 3-days after the visit date. The same assessment steps in Week 4 will apply to Week 8 (EOT) visits, with the addition that at Week 8 participants will receive instructions about how to uninstall the app and will go through other end-of-study procedures.

Not including the referral period and potential for participants to complete the last self-reported assessments 3 days after the week 8 visit, the duration of study participation is 8 weeks. [Figure 3](#) shows the overall Study Schematic.

Figure 3. Study Schematic

[figure not shown]
[figure not shown]

Sponsor Name: Woebot Health

Protocol Number: WB001-001

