7.3 SERIOUS ADVERSE EVENTS

An SAE is any AE that meets any of the following criteria:

- Results in death
- Is *life-threatening*
- Requires inpatient *hospitalization* or prolongation of existing hospitalization
- Results in persistent or significant *disability/incapacity*
- Is an *important medical event*

Sponsor Name: Woebot Health

Protocol Number: WB001-001

UNANTICIPATED ADVERSE DEVICE EFFECTS

A suspected unanticipated adverse device effect (UADE) is defined as an untoward and unintended response to a study treatment, which is not listed in the applicable product information, and meets at least one AE or SAE criterion, and is assessed as causally related to the study treatment. The Sponsor or designee will be responsible for carrying out required reporting to investigators, health authorities, and other entities as required by law.

DOCUMENTING AND REPORTING ADVERSE EVENTS AND SERIOUS ADVERSE EVENTS

Reporting of non-serious AEs and SAEs will begin at the time of first interaction with the app and will continue through EOT. Any new clinical condition or worsening of existing conditions between the time the informed consent form (ICF) is signed, and the first use of the study intervention will be recorded as AE/SAEs unrelated to the device.

AEs and SAEs may be reported spontaneously by participants, discovered as a result of general, non-leading verbal questioning by the study staff, or determined by assessments. As needed, qualified study staff will inform investigators to inquire about any new symptoms or worsening of symptoms during the telehealth visits at Weeks 4 and 8. In the interim, participants will be instructed to contact the investigator if new or worsening symptoms develop outside of key assessment visits. All incidences confirmed as AEs or SAEs will be monitored and recorded in the eCRF throughout the entire study.

The investigator must pursue and obtain adequate information about all incidences they deem as AEs and SAEs. At minimum this includes a description of the event, severity, device relatedness, start and stop times, duration, outcome, and any action (e.g., treatment/follow-up tests). The investigator must also assess whether the event meets the criteria for classification as an SAE.

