It is the investigator's responsibility to review all documentation (e.g., hospital notes, laboratory reports, and diagnostic reports) related to an AE or SAE. Whenever possible, a single unifying diagnosis should be reported as the event term, and not the individual signs and symptoms.

Investigators are not obligated to actively seek AEs or SAEs after the participant's conclusion of study participation. However, if the investigator learns of any SAE, including death, at any time after a participant has been discharged from the study, and he/she considers the event to be reasonably related to the investigational device or study participation, the investigator must promptly notify the Sponsor.

REPORTING OF SERIOUS ADVERSE EVENTS

The investigator must immediately report SAEs to the Sponsor or designee (no later than 24 hours after becoming aware of the event) using the SAE report form.

The investigator is obliged to promptly respond to any request for follow-up information (e.g., additional information, event outcome, final evaluation, or other records if needed) and to any question from the Sponsor or designee. This timely reporting is necessary to ensure prompt assessment of the event by the Sponsor or designee and to allow them to meet strict regulatory timelines associated with expedited reporting obligations for SAEs.

Sponsor Name: Woebot Health

Protocol Number: WB001-001

The Sponsor has a legal responsibility to notify both the local regulatory authority and other regulatory agencies about the safety of a study intervention under clinical investigation. The Sponsor will comply with country-specific regulatory requirements relating to safety reporting to the regulatory authority, IRB, and investigators.

An investigator who receives an investigator safety report describing an SAE or other specific safety information (e.g., summary or listing of SAEs) from the Sponsor will review and then file it along with the Investigator's Brochure and will notify the IRB, if appropriate according to local requirements.

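### AE/SAE recording closes at the Week 8 visit, but the PHQ-9 and EPDS items used to find AEs may be answered up to 3 days later, and no readable rule says how an AE found in those days is recorded or tabulated

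*Combined protocol and SAP*

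**What the plan says.** **When recording stops.** The footnotes to Appendix 3 say "AEs/SAEs should be recorded until the EOT visit". Section 7.3 says that reporting "will begin at the time of first interaction with the app and will continue through EOT", and one paragraph later that "All incidences confirmed as AEs or SAEs will be monitored and recorded in the eCRF throughout the entire study". For the time after participation ends, Section 7.3 adds: "Investigators are not obligated to actively seek AEs or SAEs after the participant's conclusion of study participation". An SAE that the investigator learns of later goes to the Sponsor only if judged reasonably related to the device or to taking part.

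**What stays open.** The Synopsis (Safety Aim) uses the C-SSRS together with "the PHQ-9 item #9, and the EPDS item #10, and the HAM-D17 item #3 to facilitate identification of AEs and SAEs". The PHQ-9 and EPDS are self-report links with a window of 3 days either side of the visit date (Synopsis, Section 3.1, Appendix 3). Section 3.1 gives participation as 8 weeks, leaving out the "potential for participants to complete the last self-reported assessments 3 days after the week 8 visit".

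**What happens to a flag.** Under Section 5.3, a score above the stated threshold on either item alerts the investigator, who reviews it and follows up within 24 hours. No cut-off at the Week 8 visit is given.

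**What is tabulated.** Section 9.5 selects AEs by onset date: from first use of the device, and before the date of last use. Section 9.4 compares AEs and SAEs between arms.

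**The concern.** Two of the instruments that feed AE identification can produce a signal after the recording period has closed. A site that follows the schedule of events would act on the flag, confirm an event and then find that the recording rule had already ended. A site that follows the whole-study sentence in Section 7.3 would enter the same event. The AE record would then depend on which sentence a site reads.

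AEs and SAEs are safety endpoints compared between arms, and suicidal ideation is among the concerns that Section 7 anticipates in this population. The tabulation rule adds a second gap, because an event that is properly recorded can still drop out of the tables if it began on or after the day the app was last used.

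**Working it through.** The plan gives no figure to reproduce. The check compares the rules and counts days.

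**Inputs**
- Close of recording: the EOT visit (Appendix 3); EOT, and also the entire study (Section 7.3).
- Self-report window: visit day V, from V−3 to V+3 (Section 3.1, Appendix 3).
- Recall: PHQ-9 2 weeks, EPDS 7 days (Section 5.2).
- Follow-up of a flag: within 24 hours (Section 5.3).
- Tabulation: onset before the date of last use (Section 9.5). Instructions for uninstalling the app are given at Week 8 (Section 3.1), but the date of last use is not fixed.

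**Step 1. Can a post-visit flag concern an event that began by the visit?** Count days inclusively, with completion on V+3.

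| Scale | Recall | Days covered | On or before V | After V |
|---|---|---|---|---|
| PHQ-9 | 14 days | V−10 to V+3 | 11 | 3 |
| EPDS | 7 days | V−3 to V+3 | 4 | 3 |

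For a visit on Day 56 and a PHQ-9 on Day 58, recall runs over Days 45 to 58, and 12 of those 14 days are on or before the visit. So a late flag often looks back into the treatment period.

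**Step 2. When could such an event be confirmed?** A questionnaire completed on V+3 and followed up within 24 hours gives confirmation as late as V+4 (3 + 1 days).

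**Step 3. What do the rules do with an event first confirmed after V?**

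| Onset | Appendix 3, read literally | Section 7.3, whole-study sentence | Section 9.5 tables |
|---|---|---|---|
| By V, and before last app use | Not recorded | Recorded | Eligible, but only if recorded |
| By V, but on or after last app use | Not recorded | Recorded | Excluded |
| V+1 to V+3 | Not recorded | Recorded | Excluded if app use ended by V (an assumption) |

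The first row is the clearest loss: the event belongs in the tables, and only the footnote keeps it out. The second and third rows show that changing the footnote alone is not enough, because Section 9.5 would still exclude those events.

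**The case against.** The strongest reply is that the protocol already captures these events. Section 7.3 has confirmed events recorded throughout the study. Section 7 has suicidal ideation events recorded and raised to AE or SAE status where appropriate. Section 11 has contacts yielding significant clinical information documented and entered, and Section 11.2 requires eCRF completion within 5 business days of any participant evaluation or communication. The abbreviations under Table 1 define EOT as an assessment, which could include the late self-reports. These points show that the intention may well be to record such events. They do not settle the matter, because Appendix 3 names the EOT visit as the end point and so conflicts with the broader sentences.

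The escalation scenarios in Section 5.3 and Appendix 3 are blacked out and might cover late flags. That limits certainty about what the full plan contains, but the readable passages would still disagree.

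A reader might infer that all late flags fall outside the safety comparison. The documents do not support that. A flag date is not an onset date, Section 9.5 selects by onset, both scales look back past the visit, and a flag becomes an AE only on the investigator's judgement (Section 7). Nor is Week 8 safety left to the late links: the C-SSRS, HAM-D17 item 3 and an AE/SAE assessment are also scheduled then.

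Two further inferences go too far. Nothing in the documents suggests that one arm completes its links later than the other. And although the Benefit/Risk Assessment lists loss of app access at Week 8 as a possible source of brief stress, 3 more days of recording would hardly observe it. It is not a ground for this change.

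**Conclusion.** The recording rule and the self-report window do not match, and Section 7.3 contradicts the schedule of events on when recording ends. Under the literal footnote, an AE first confirmed from a post-visit PHQ-9 or EPDS goes unrecorded even if it began before the visit. Separately, Section 9.5 excludes from the tables any event starting on or after the date of last device use. Follow-up of the participant is not lost.

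The size cannot be computed. It is tempting to spread completion evenly over the 7-day window, which would put 3/7 (43%, about 90 of 210 participants) after the visit. But the documents give no distribution of completion times, flag rate or share of flags confirmed as AEs, and 210 assumes no dropout. That figure should not be read as an estimate, and it would count late questionnaires, not lost AEs.

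The mismatch itself rests on the text alone. That events starting after the visit also miss the tables rests on the assumption that app use ends at or before the Week 8 visit. This is an inexpensive improvement to safety capture, not a flaw that threatens the trial.

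**What to change.** Reconcile Sections 3.1, 7.3, 9.5 and Appendix 3 into one window:

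- **Recording (Appendix 3, Section 7.3):** AEs and SAEs are recorded until the later of the EOT visit and completion of the last Week 8 ePRO, which may be up to 3 days after the visit. Any event confirmed by the follow-up of a flag on such an ePRO is included, even where confirmation comes the next day. The whole-study sentence in Section 7.3 should refer to this window.
- **End of participation (Section 3.1):** align with the same end point, so that the post-participation rule in Section 7.3 does not begin before the last ePRO is in.
- **Tables (Section 9.5):** include events with onset through the end of this window, instead of stopping before the date of last use. Without this, late events would be recorded and then left out.

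The cost is amendment wording, a changed EDC date check and at most 3 more days of AE recording per participant (3/56, about 5% of the 8-week period). It needs no new visit or assessment and changes no clinical rule; the response to flags in Section 5.3 stays as written.
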